## **AIM 2. Feasibility study of Peer plus**

Knowledge gained from the usability study will be used to revise the Peers plus intervention manual and we will conduct a feasibility study with 20 ethnic minority, community-dwelling older adults with depression. In this study, recruitment, and enrollment procedures as well as eligibility criteria will be identical to the usability study in Aim 1. For the feasibility study, the duration of the Peers plus intervention will be 8 weeks with identical intervention content and process. Data collection procedures will consist of assessment at baseline assessment, post-study assessment and a 3 month follow-up. We will conduct a post-study semi-structured interview.

## **Data collection**

### Quantitative data

Listed in Table 3 is the timeline of study measures for the usability and feasibility studies. Data obtained from participants recruited for this protocol will include sociodemographic information (e.g., age, race, ethnicity, etc.), attitudes toward technology and technology use, self-reported clinical information (past history of depression services, current mental health service use), self-reported psychosocial measures (physical, social and emotional function, depression, self-efficacy, coping and loneliness) and social determinants of health. We will measure engagement defined in two ways: 1) as attendance of 80% of meetings as reported by peer mentors  and 2) score on the Working Alliance Inventory-SR.

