**to meet mental health service needs of participants with depression and link them to professional care as needed.**

## **Preliminary studies**

**1. Feasibility and acceptability of a peer support intervention for depression.** We developed a peer support intervention and evaluated the feasibility and acceptability of peer support for participants. We examined participant and peer experiences of the program. We found that engagement was high (90% percent of participants attended all 8 meetings with the peer). The majority was African American participants (74%) and 85% had decrease in PHQ-9 scores [Mean 7.1 (SD 7.1) p-value < 0.001]. Loneliness decreased (pre-study mean  $36.7 \pm 5.4$ ; post-study mean  $31.4 \pm 16.7$ , p-value 0.03) and coping skills increased (pre-study mean  $65.6 \pm 13.2$ , post-study mean  $69.9 \pm 10.4$ , p-value 0.006). Participants emphasized the importance of a trusting relationship, credibility of the peer and usefulness of professional supervision in the program. Participants described benefits such as hope, changes in attitude, behavior, and insight. The program also successfully connected participants to community and clinical resources during and after the study. We successfully contacted 85% of patients at 12 months and assessed depression with the PHQ-9 by telephone. Sixty-eight percent of patients had PHQ-9 scores that remained below baseline scores by 5 points or more. After completion of the feasibility study, we recruited 27 additional participants (total of 57 participants) seeking to obtain greater experience with a larger sample of peers and participants to refine the peer program. We tried telephone delivery of the program for two participants. Although peers found the telephone convenient, relationship building was more difficult, and two participants missed telephone calls more frequently but attended in-person meetings regularly. Given the importance of problems of loneliness among our study participants, we continued with in-person meetings and used telephone calls infrequently when peers were unable to meet in person due to weather. We concluded that use of supervised peer mentors is a promising model of depression care delivery for participants. We conducted an analysis using data from 57 participants in the pilot study to assess whether self-efficacy predicted change in depression. We found that improvement in self-efficacy was associated with a decline in depression.

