## **Aim 2. Feasibility study**

**Quantitative assessments** The RA will conduct a baseline assessment that includes demographic information (e.g. age, ethnicity, gender, education), self-report measures on depression, medical comorbidity, social determinants of health, self-efficacy, loneliness, coping skills, social, physical, and emotional functioning, technology use and attitudes (see Table 3 below). The peer mentor will fill out a Working Alliance Inventory on a weekly basis to assess the quality of the bond, agreement on tasks and goals. Background analytical information on various factors will be collected, including frequency and duration of zoom use, number of messages sent, number of video calls, and time spent on video calls.

**Qualitative data** We will conduct a semi-structured interview lasting approximately 45 minutes with the peer mentors and participants upon completion of the intervention at 8 weeks by zoom. We will gather information about satisfaction with the interactions with the peer using the video chat. The purpose will be to understand peer and participant experience in the intervention. The interviews will be audio recorded, professionally transcribed and themes extracted using a thematic analytic framework.

Table 3. Assessments	
Variable	Measure
Demographic information	Age, gender, ethnicity, education, marital status, mental health history
Depression (self-report)	PHQ-9  a widely used, self-report instrument that is keyed to DSM-IV-R criteria for Major Depression
Physical, social and emotional function	Medical Outcomes Study Short Form 36  10 item measure of overall health, composed of sub-sections that assess emotional, physical and social functioning,
Medical comorbidity	Medical comorbidity will be measured with the WHO WMH CIDI that has been established for use among older adults and has proven validity and reliability. 

Mass General Brigham Institutional Review Board  
Intervention/Interaction Detailed Protocol

---

Coping skills	The Brief Cope is widely used in depression studies which assesses trait and state coping developed from the COPE inventory which assesses different coping dimensions. 
Self-efficacy	General Self-efficacy Scale  10-item measure that has been used among participants and found to be sensitive to changes in psychosocial interventions for depression.

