**Study:**

Feasibility pilot study with approximately 32 participants  
Preliminary analysis of primary (PHQ-9) and secondary outcomes.

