# Model 2 adjusted for age, gender, education, marital status, race, and employment status.

## Model 3 adjusted for demographic variables and loneliness.

Self-Efficacy

Model	Timepoint	Estimate	Std. Error	95% CI	p-Value	Effect Size(standardized coefficients)	Marginal R^2
Model 1: Basic	Baseline vs Poststudy	2.030	0.824	(0.375, 3.686)	0.017	0.40	0.051
	Baseline vs 3-mons follow-up	2.773	0.870	(1.024, 4.521)	0.003	0.55	
Model 2: Adjusted for demographics #	Baseline vs Poststudy	2.018	0.823	(0.363, 3.673)	0.018	0.40	0.383

	Baseline vs 3-mons follow-up	2.773	0.872	(1.021, 4.525)	0.003	0.55	
Model 3: Full	Baseline vs Poststudy	1.823	0.760	(0.295, 3.351)	0.020	0.48	0.566
	Baseline vs 3-mons follow-up	2.318	0.799	(0.711, 3.926)	0.006	0.55	

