# Model 2 adjusted for age, gender, education, marital status, race, and employment status.

## Model 3 adjusted for demographic variables and loneliness.

#### Emotional Well-being

Model	Timepoint	Estimate	Std. Error	95% CI	p-Value	Effect Size(standardized coefficients)	Marginal R^2
Model 1: Basic	Baseline vs Poststudy	6.571	2.668	(1.208, 11.935)	0.017	0.32	0.057
	Baseline vs 3-mons follow-up	12.566	2.869	(6.801, 18.330)	0.000	0.61	
Model 2: Adjusted for demographics #	Baseline vs Poststudy	6.571	2.663	(1.220, 11.923)	0.017	0.32	0.215
	Baseline vs 3-mons follow-up	12.293	2.870	(6.526, 18.060)	0.000	0.60	
Model 3: Full	Baseline vs Poststudy	5.375	2.593	(0.159, 10.591)	0.044	0.26	0.289
	Baseline vs 3-mons follow-up	11.119	2.784	(5.519, 16.720)	0.000	0.54	

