# Model 2 adjusted for age, gender, education, marital status, race, and employment status.

## Model 3 adjusted for demographic variables and loneliness.

#### Social Function

Model	Timepoint	Estimate	Std. Error	95% CI	p-Value	Effect Size(standardized coefficients)	Marginal R^2
Model 1: Basic	Baseline vs Poststudy	5.804	4.656	(-3.557, 15.164)	0.219	0.20	0.068

	Baseline vs 3-mons follow-up	18.775	4.994	(8.740, 28.809)	0.001	0.65	
Model 2: Adjusted for demographics #	Baseline vs Poststudy	5.804	4.648	(- 3.539, 15.146)	0.218	0.20	0.304
	Baseline vs 3-mons follow-up	18.385	5.004	(8.329, 28.441)	0.001	0.64	
Model 3: Full Model ##	Baseline vs Poststudy	5.926	4.612	(- 3.350, 15.202)	0.205	0.21	0.385
	Baseline vs 3-mons follow-up	16.447	4.944	(6.504, 26.390)	0.002	0.57	

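### Three of the six psychosocial measures other than PHQ-9 (physical function, coping, loneliness) have no outcome table in the SAP, and no secondary-outcome list or stated reason explains the gap

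*Protocol*

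**What the plan says.** - **Collected.** Protocol, Data collection, Quantitative data: "self-reported psychosocial measures (physical, social and emotional function, depression, self-efficacy, coping and loneliness". The Aim 2 feasibility section repeats the battery for the baseline assessment: depression, then "self-efficacy, loneliness, coping skills, social, physical, and emotional functioning, technology use and attitudes".
- **Visits.** Protocol, Aim 2 (Feasibility study of Peer plus), gives baseline, post-study and 3-month assessments without saying which measures are taken at each. Table 3 is described as giving the timeline, but as available here it shows no visits.
- **Planned inference.** Protocol, Statistical and Qualitative Analysis, plans inferential analysis of depressive symptoms only. It adds that the quantitative data will be used to find factors related to engagement and depression reduction.
- **SAP scope.** The Study section reads "Preliminary analysis of primary (PHQ-9) and secondary outcomes". No secondary outcome is named there or elsewhere.
- **SAP methods.** The multilevel model is described for the primary outcome. Baseline loneliness is listed among its covariates. Paired t-tests and Wilcoxon tests are said to have been run on outcome measures that are not named, and no results from them are shown.
- **SAP results.** Model tables appear for PHQ-9, "Self-Efficacy", "Emotional Well-being" and "Social Function". The notes under each say "Model 3 adjusted for demographic variables and loneliness".
- **Pilot.** Protocol, Preliminary studies, reports pre/post change in loneliness ("Loneliness decreased (pre-study mean" 36.7, post-study 31.4, p = 0.03) and in coping (65.6 to 69.9, p = 0.006).

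**The concern.** When some measures in a battery are modelled and others are not, and nothing written beforehand says which were to be modelled, the reader has no basis for judging the pattern. Here every measure shown has a significant 3-month contrast, so the picture is one of broad benefit. Three null or adverse results would change that picture, and the documents neither give them nor rule them out.

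The omitted measures are not peripheral. Sharing coping skills is a core part of the intervention. The pilot kept to in-person meetings partly because of loneliness, and this study moves delivery to video. Physical function belongs to the same instrument as two outcomes that are shown.

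**Working it through.** **1. Match the measures to the tables.** I take the SAP's emotional well-being to be the protocol's emotional function.

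| Measure (Protocol, Quantitative data) | Instrument (Protocol, Table 3) | SAP outcome table | Model 1 p, post-study / 3 months |
|---|---|---|---|
| Depression | PHQ-9 | yes (primary) | 0.018 / 0.001 |
| Self-efficacy | General Self-efficacy Scale | yes | 0.017 / 0.003 |
| Emotional function | Medical Outcomes Study short form | yes | 0.017 / 0.000 |
| Social function | same short form | yes | 0.219 / 0.001 |
| Physical function | same short form | none | not shown |
| Coping | Brief COPE | none | not shown |
| Loneliness | R-UCLA Loneliness Scale | none (covariate only) | not shown |

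Without a table: 7 − 4 = 3, which is 3/7 = 43% of all measures, or 3/6 = 50% once the primary is set aside. By instrument, 3 of 5 contribute at least one table and 2 contribute none.

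**2. Check the printed tables.** There are 4 outcomes × 2 visits × 3 models = 24 tests. Recomputing p from estimate/SE, with a t distribution on an assumed 50 degrees of freedom, reproduces all 24 to within about 0.001. For example, PHQ-9 in Model 1 at 3 months gives −2.88/0.83 = −3.47, p = 0.0011, against 0.001 printed. What is shown is internally consistent. Of the 24, 21 have p < 0.05; the other three are post-study social function (0.219, 0.218, 0.205).

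**3. What the missing measures would add.** This is for scale only: the SAP sets no multiplicity rule, and independence is assumed. Non-primary contrasts per model go from 3 × 2 = 6 to 6 × 2 = 12.
- Chance of at least one false positive at 0.05 each: 1 − 0.95^6 = 26.5%, rising to 1 − 0.95^12 = 46.0%.
- Bonferroni threshold: 0.05/6 = 0.00833, falling to 0.05/12 = 0.00417.
- Self-efficacy at 3 months in Model 3 (p = 0.006) meets the first threshold and misses the second. The three Model 1 results at 3 months (0.003, 0.000, 0.001) meet both.

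**4. Could picking from null measures produce the printed results?** Suppose none of the six non-primary measures truly changed. If they are independent, the chance that three or more reach p ≤ 0.003 is about C(6,3) × 0.003³ = 20 × 2.7×10⁻⁸ = 5.4×10⁻⁷. Under any dependence, Markov's inequality bounds it at 6 × 0.003/3 = 0.006. A partial display could hide null measures; it does not readily explain the three results that are shown.

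**5. Which loneliness value is in Model 3?** The methods text says baseline; the table notes do not say. Percentage change in the estimate:

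| Outcome | Post-study, Model 1→2 | Post-study, Model 2→3 | 3 months, Model 1→2 | 3 months, Model 2→3 |
|---|---|---|---|---|
| PHQ-9 | 0.0 | −7.8 | −2.4 | −13.9 |
| Self-efficacy | −0.6 | −9.7 | 0.0 | −16.4 |
| Emotional well-being | 0.0 | −18.2 | −2.2 | −9.6 |
| Social function | 0.0 | +2.1 | −2.1 | −10.5 |

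Covariates fixed within a participant can move a within-participant contrast only through missing data, and adding the demographics moves it by at most 2.4%. Adding loneliness moves it by 2.1% to 18.2%. I also simulated 150 trials of 32 participants with assumed parameters and 15% missing at 3 months only. A baseline-only covariate left the post-study estimate unchanged and moved the 3-month estimate by a median of 1.3% (90th percentile 4.7%). The printed shifts therefore suggest a time-varying value, but missing loneliness data could also produce them.

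**The case against.** A reader might infer that the four outcomes were picked because they came out well. The documents do not support that. Post-study social function is printed as non-significant in all three models, PHQ-9 was the declared primary, and step 4 shows that picking from nulls is a poor explanation of the rest. No prespecified list was breached either, because none exists.

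A reader might also infer that loneliness was wrongly demoted from outcome to covariate. The protocol's analysis section looks for factors related to depression reduction, and the SAP text names baseline loneliness as a covariate, so that use fits the plan. The pilot reported change in loneliness and coping but does not bind this study.

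Three further objections have force:
- The SAP's unnamed summaries and paired tests may have covered the three measures. What is established is that no outcome table is shown, not that nothing was analysed.
- Neither document states that these three were measured after baseline. That is equally true of the three secondary outcomes that were modelled.
- This is a feasibility study, the SAP calls its analysis preliminary, and it already contains results. Any list of secondary outcomes written now is retrospective.

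These points limit the claim and make the remedy conditional. None of them supplies the missing results or a reason for leaving them out.

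**Conclusion.** The point holds as an unexplained subset, not as proven selection. Of the six psychosocial measures other than PHQ-9, three (50%) have no outcome table, and neither document names the secondary outcomes or explains the omission. The secondary results are therefore open to selective-reporting bias of unknown direction and size. No corrected estimate can be given, because the documents hold no results for the three measures in this study. The primary PHQ-9 result is not affected by the omission.

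The count rests on reading emotional well-being as emotional function and on treating the three function domains as separate measures, as the protocol's list does. That loneliness entered Model 3 as a time-varying value is a plausible inference only. If it did, post-baseline loneliness data exist, and adjusting for them could remove part of the change being estimated.

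**What to change.** 1. List every secondary outcome with its visits.
2. Where post-study and 3-month data were collected, fit the existing Model 1 to physical function, coping and loneliness. Report all seven measures at both visits in one table (7 × 2 = 14 contrasts), whatever the results. Where a measure was taken at baseline only, say so.
3. Label all secondary results exploratory and say that the list was completed after results were available.
4. State whether loneliness in Model 3 is the baseline or a time-varying value, and make the methods text and the table notes agree.

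The cost is three more runs of a model already in use and some added text. The overall picture may become less favourable.

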### **Aim 1 Usability study**

Quantitative data A baseline assessment will be conducted by the RA with participants recruited for this protocol. Baseline assessments will include demographic information (e.g. age, ethnicity, gender, education). We will use self-report measures to collect information on depression, medical comorbidity, social determinants of health, self-efficacy, loneliness, coping skills, social, physical, and emotional functioning, attitudes toward technology and technology use. **Assessments at 2 and 4 weeks.** With both the peer mentor and participant at 2 and 4 weeks, we will collect measures of usability with a widely used self-report scale (i.e. System Usability Scale (SUS), an objective measure of user engagement with the texting and video

chatting system (i.e. background analytics of supportive texting). This measure is a simple, ten-item Likert scale with five response options that measures the perception of usability by users. Background analytical information on various factors will also be collected, including frequency and duration of platform use, number of messages sent, word count in messages, number of video calls, and time spent on video calls.

**Qualitative data** We will conduct a semi-structured interview with the peer mentors and participants at 2 weeks and 4 weeks. The study staff will assess peer and participants' experiences with sending and receiving texts, the content and wording, the timing and frequency of the text messages received and engagement with the texting system. We will gather information about satisfaction with the interactions with the peer using the video chat. Consistent with the user-centered design principle of ideation, qualitative and quantitative data collected will be used to revise the intervention. The interviews will be audio recorded, professionally transcribed and themes extracted regarding user experience.

## **Aim 2. Feasibility study**

**Quantitative assessments** The RA will conduct a baseline assessment that includes demographic information (e.g. age, ethnicity, gender, education), self-report measures on depression, medical comorbidity, social determinants of health, self-efficacy, loneliness, coping skills, social, physical, and emotional functioning, technology use and attitudes (see Table 3 below). The peer mentor will fill out a Working Alliance Inventory on a weekly basis to assess the quality of the bond, agreement on tasks and goals. Background analytical information on various factors will be collected, including frequency and duration of zoom use, number of messages sent, number of video calls, and time spent on video calls.

**Qualitative data** We will conduct a semi-structured interview lasting approximately 45 minutes with the peer mentors and participants upon completion of the intervention at 8 weeks by zoom. We will gather information about satisfaction with the interactions with the peer using the video chat. The purpose will be to understand peer and participant experience in the intervention. The interviews will be audio recorded, professionally transcribed and themes extracted using a thematic analytic framework.

Table 3. Assessments	
Variable	Measure
Demographic information	Age, gender, ethnicity, education, marital status, mental health history
Depression (self-report)	PHQ-9  a widely used, self-report instrument that is keyed to DSM-IV-R criteria for Major Depression
Physical, social and emotional function	Medical Outcomes Study Short Form 36  10 item measure of overall health, composed of sub-sections that assess emotional, physical and social functioning,
Medical comorbidity	Medical comorbidity will be measured with the WHO WMH CIDI that has been established for use among older adults and has proven validity and reliability. 

Mass General Brigham Institutional Review Board  
Intervention/Interaction Detailed Protocol

---

Coping skills	The Brief Cope is widely used in depression studies which assesses trait and state coping developed from the COPE inventory which assesses different coping dimensions. 
Self-efficacy	General Self-efficacy Scale  10-item measure that has been used among participants and found to be sensitive to changes in psychosocial interventions for depression.
Loneliness	R-UCLA Loneliness Scale  a commonly used, 20-item, self-report questionnaire. 
Technology use and attitudes on technology	Questions adapted from a validated survey assessing technology and media usage and attitudes 
Working alliance	Working Alliance Inventory-Short Revised -a short 7-item questionnaire that measures affective bond, agreement on tasks and goals, and has been used to measure working alliance in non-professional relationships in mental health. 
User experience (in usability study only)	System Usability Testing  10 item survey for measuring assessments of systems usability.

Only trained study staff will have access to these data. Participants' data will be identified by an ID number only, and a link between names and ID numbers will be kept separately under lock and key. Staff will have a password-protected account for downloading the data. All PM-participant meetings will be audio-recorded to ensure fidelity. The MHP will review the recordings and provide feedback during weekly supervision (e.g., problem solve challenging cases). All study staff will have up-to-date Collaborative Institutional Training Initiative (CITI) certifications. All data will be collected by telephone and zoom. To protect participants' confidentiality, we will not use participants' names during supervision meetings of peer mentors.

### **Standard of care**

Participants will be informed during the clinical assessment and reminded throughout the study that professional mental health care is the standard of care for depression. PMs are persons who have had positive experiences in depression treatment and are trained to encourage professional mental health care use in study participants. At any point, if the participants express desire for information or referral to professional mental health care, the study will provide that.

